9 SAMPLE SIZE AND POWER CONSIDERATIONS

A sample size of 22 patients per treatment group (avacopan and placebo, respectively) in each of the C5b-9 level strata is based on the between-treatment difference of -35% in the C3G

Histologic Index for activity at Week 26, standard deviation (SD) 34%, power 90%, and 2-sided $\alpha = 0.05$.

The sample size of 22 per group also provides approximately 90% power to detect a delta of -35% in the C3G Histologic Index for activity between the percent change from baseline in the first 26 weeks and in the second 26 weeks, assuming an SD of 34% for each change. The mean treatment effect size of 35% is considered reasonable based of the following:

- Of the 5 patients with histologic data in the study by Herlitz et al., 2012 with eculizumab, an anti-C5 antibody, 2 patients had a 67% decrease (improvement) in histologic score, 1 had a 43% decrease, and 2 had no change from baseline; the mean decrease for the 5 patients was 35%;
- An improvement in the histologic score of at least 35% is considered clinically meaningful by clinical and histology experts;
- The SD for the percent change from baseline in C3G Histologic Index of activity was 34% in the Herlitz study; a change of 35% of greater will be above the observed variance for this parameter.

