As specified in the [Time and Events Table](#), blood and urine samples will be collected for safety, efficacy, and pharmacokinetic and biomarker measurements. A serum pregnancy test for women of childbearing potential will be done regularly during the 52-week treatment period and at the end of the 8-week follow-up period. Liver function and hematology including differential blood work will be monitored at least every 4 weeks throughout the study. Physical examinations and vital signs assessments will be performed throughout the study. Health-related quality of life using the EQ-5D-5L and SF-36 v2 surveys will be assessed periodically over the course of the study. Study drug (avacopan or placebo) will be dispensed and drug accountability will be done. Concomitant medication and adverse event assessments will be made at every study visit. A follow-up renal biopsy will be performed at the following time points:

1. Within 2 weeks prior to the Week 26 visit, and should be completed before open-label medication is started;
2. If a patient is withdrawn early from the study, and
3. After the 52-week treatment period.

The Week 52 biopsy is optional in adolescent patients.

If a patient is on other immunosuppressive or glucocorticoid treatment at the start of dosing, the dose(s) of concomitant immunosuppressive or glucocorticoid treatment may not be increased during the study (see [Section 5.9](#)). Treatment with these other drugs may be reduced or stopped during the study at the discretion of the Investigator, if the patient's condition justifies it.

Adjustments of tacrolimus and cyclosporine doses to ensure these medications are at goal trough levels for maintenance of immunosuppression in transplant patients will be allowed during the study. No new treatments for C3G, except for renin-angiotensin-aldosterone system (RAAS) inhibitors, may be added during the study period (52-week treatment period or 8-week follow up), unless the patient's condition deteriorates to the extent that the investigator deems it in the best interest of the patient to do so. Addition of new treatments for C3G during the treatment period will be considered a treatment failure.

Patients who experience deteriorating renal function based on an increase in serum creatinine of at least 50%, or an increase in proteinuria of >3 g/g creatinine from Screening or baseline during

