4. STUDY POPULATION

4.1. Size of the Population

The aim is to enroll approximately 88 patients in this clinical trial with approximately 44 patients in each of the two C5b-9 level strata. Patients who drop out early will not be replaced.

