8.8. Sample Size Justification

A sample size of 22 patients per treatment group (avacopan and placebo, respectively) in each of the C5b-9 level strata is based on the between-treatment difference of -35% in the C3G Histologic Index for activity at Week 26, standard deviation (SD) 34%, power 90%, and 2-sided $\alpha = 0.05$.

The sample size of 22 per group also provides approximately 90% power to detect a delta of -35% in the C3G Histologic Index for activity between the percent change from baseline in the first 26 weeks and in the second 26 weeks, assuming an SD of 34% for each change.

The mean treatment effect size of 35% is considered reasonable based of the following:

- Of the 5 patients with histologic data in the study by [Herlitz et al., 2012](#) with eculizumab, an anti-C5 antibody, 2 patients had a 67% decrease (improvement) in histologic score, 1 had a 43% decrease, and 2 had no change from baseline; the mean decrease for the 5 patients was 35%;
- An improvement in the histologic score of at least 35% is considered clinically meaningful by clinical and histology experts;
- The SD for the percent change from baseline in C3G Histologic Index of activity was 34% in the Herlitz study; a change of 35% of greater will be above the observed variance for this parameter.

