5.2.2 Secondary Analysis

The same analysis as described for the primary analysis will also be performed for the following:

- Percent change and change from baseline to Week 26 during the placebo-controlled, double-blind treatment period in the combined C5b-9 strata (subjects with elevated C5b-9 blood levels and non-elevated C5b-9 blood levels).
- Percent change and change from Week 26 to Week 52 during the avacopan treatment period in the elevated C5b-9 stratum
- Percent change and change from Week 26 to Week 52 during the avacopan treatment period in the combined C5b-9 strata (subjects with elevated C5b-9 blood levels and non-elevated C5b-9 blood levels).

For percent change and change from Week 26 to Week 52, observed data at Week 26 and Week 52 will be used in the primary analysis and will be conducted in patients who completed Week 26 and Week 52 renal biopsies. The percent change from Week 26 to Week 52 will be only analyzed for subjects for whom the Week 26 activity index score is not 0. Multiple imputation methods similar to the primary endpoint at Week 26 may be explored.

Since the placebo group in Treatment Period A will receive avacopan during the second 26 weeks of the study, the percent change from Week 26 to Week 52 in the C3G Histologic Index for activity in the placebo control group will be compared to the percent change from baseline to Week 26 in the same group. This analysis will be done by the paired t-test. Point estimates and corresponding 95% confidence intervals will be estimated for the difference between the second 26 weeks (avacopan treatment) and the first 26 weeks (placebo treatment). This same analysis will be performed in the avacopan treatment group, comparing percent change from Week 26 to Week 52 in the C3G Histologic Index for activity in the avacopan treatment group to the percent change from baseline to Week 26 in the avacopan treatment group. These analyses will be carried out in the ITT population in the elevated C5b-9 stratum (>244 ng/ml) and separately for the combined C5b-9 strata. These analyses will require non-missing data at Baseline, Week 26 and Week 52. The same analyses will be carried out for change from baseline.

The SAS code to generate the paired t-test will be similar to the following:

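### Does the SAP's 90% power for the first-versus-second 26-week comparison need restating, and does the combined-strata test need its own sample size basis?

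*SAP*

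**What the plan says.** SAP Section 9 carries over the text of Protocol 8.8. The planned 22 patients per arm "in each of the C5b-9 level strata is based on the between-treatment difference" of −35% in the activity index at Week 26, with SD 34%, 90% power and two-sided alpha 0.05. Then: "The sample size of 22 per group also provides approximately 90% power to detect a delta of" −35% between the percent changes of the two 26-week periods, "assuming an SD of 34% for each change".

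SAP 5.2.2 specifies the analysis behind this second claim. By paired t-test, the Week 26 to Week 52 percent change "in the placebo control group will be compared to the percent change from baseline to Week 26 in the same group". It also states the data rule: "These analyses will require non-missing data at Baseline, Week 26 and Week 52". The test is run in the elevated stratum "and separately for the combined C5b-9 strata", with point estimates and 95% confidence intervals. A patient whose Week 26 score is 0 has no analysable percent change for the second period.

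Two design features bear on how many complete sets there will be. Protocol 3.4: "The Week 52 biopsy is optional in adolescent patients". Protocol 4.1: "Patients who drop out early will not be replaced".

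On the testing order, SAP 3.1 tests the elevated stratum first and the combined strata second. SAP 3.2.5.2 and Section 10 limit the non-elevated stratum to summaries because it is small, and Section 10 records this as a change from the protocol.

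**The concern.** A paired t-test is driven by the SD of each patient's difference between the two changes. Section 9 gives only the SD of each change, so a reader cannot recover the 90% without supplying a correlation.

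Zero is not an obvious value for it. The Week 26 biopsy closes the first change and opens the second, so reading or sampling error in that one biopsy pushes the two changes in opposite directions. That favours a negative correlation and lower power. The claim also assumes that no biopsy set is lost, while the plan names several ways to lose one.

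Separately, Section 9 still describes a 22-per-arm test in a stratum that will not be tested. It gives no size, effect or power for the combined-strata test that now holds second place in the alpha-controlled sequence. If these gaps hid a real shortfall, a null period comparison would be read with too much confidence and a confirmatory test would lack a planning basis.

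**Working it through.** **Inputs from SAP Section 9:** n = 22, δ = 35, SD of each change = 34, two-sided α = 0.05. The correlation ρ, the number of complete sets and the size of the non-elevated stratum are not in the documents; every value below for these is an assumption.

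**1. Reproducing the stated figure.** SD of the difference = 34 × √(2(1 − ρ)). At ρ = 0 this is 34 × √2 = 48.1. Noncentrality = 35 × √22 / 48.1 = 3.41 on 21 df, and the noncentral t gives power 0.902. The between-arm test with 22 per arm has the same noncentrality, 35 / (34 × √(2/22)) = 3.41, on 42 df, and power 0.915. The paired claim is therefore the between-arm calculation carried across with independent changes, and it is arithmetically right.

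**2. Effect of correlation and of lost sets.**

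| Assumed ρ | SD of difference | 22 sets | 20 sets | 18 sets |
|---|---|---|---|---|
| +0.25 | 41.6 | 0.964 | 0.946 | 0.919 |
| +0.1 | 45.6 | 0.929 | 0.902 | 0.866 |
| 0 | 48.1 | 0.902 | 0.870 | 0.829 |
| −0.1 | 50.4 | 0.874 | 0.837 | 0.792 |
| −0.25 | 53.8 | 0.829 | 0.789 | 0.740 |
| −0.5 | 58.9 | 0.758 | 0.713 | 0.662 |

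At ρ = 0, 21 sets give 0.887. So 22 sets are not a general requirement: 20 are enough at +0.1 and 18 at +0.2 (0.902).

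**3. What sign to expect.** For raw scores with equal variance at the three biopsies, correlation r between neighbouring biopsies and r₂ between the outer two, the correlation of successive changes is (2r − 1 − r₂) / (2(1 − r)). If r₂ = r it equals −0.5. If r₂ = r² it equals −(1 − r)/2, which is −0.25 at r = 0.5 and −0.05 at r = 0.9. Patients who keep improving or worsening at their own rate push it upward. Percent changes also use different denominators in the two periods, so these values do not transfer exactly. Negative is plausible; the size is unknown.

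**4. The combined-strata test.** Take 22 elevated plus k non-elevated patients per arm. With δ = 35 and SD 34 in both strata, power is 0.915 at k = 0, 0.960 at k = 5 and 0.998 at k = 22. It cannot fall below the primary test unless the effect is smaller in the non-elevated stratum. With k = 5 and simulated trials analysed by two-sample t-test, power is about 0.92 if the effect there is half and about 0.84 if there is none. SAP 3.1 makes this test confirmatory only after the elevated stratum is significant. Given that, the chance of significance is about 0.99, 0.97 and 0.90 for full, half and no effect; the chance of passing both tests with no effect there is about 0.83.

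**The case for a change.** The best case for acting is that the period comparison is one of only two power claims in Section 9 and its hidden assumption leans the optimistic way. A shared middle biopsy favours a negative correlation, and every named source of loss (optional adolescent biopsies, no replacement, Week 26 scores of 0, biopsies blocked by COVID-19) lowers the number of sets. Together, 18 sets at ρ = −0.25 give 74%. The sponsor also knew, when writing the SAP, that the non-elevated stratum was small, yet left Section 9 unrevised for a test that carries alpha. A few sentences would cure both.

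Part of this stands. The correlation is unstated, the complete-data rule in SAP 5.2.2 is not carried into the power statement, and Section 9 is out of step with SAP 3.1. What does not stand is that the 90% is wrong: the documents contain neither a correlation nor a loss rate, and a modest positive correlation keeps power at 90% with fewer sets. Nor do they give the number enrolled in the non-elevated stratum. SAP 2.2.2 and Section 8 allow it to close early, and the SAP says only that it is small.

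**Conclusion.** No change is called for. The 90% is correct for 22 complete sets and uncorrelated changes. Its real value could be higher or lower: from 96% to 76% for assumed correlations of +0.25 to −0.5 with 22 sets, and 83% with 18 sets at zero correlation.

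Nothing in the analysis turns on that number. The paired comparison is a secondary analysis outside the gate-keeping sequence, SAP Section 8 treats the post-Week-60 analysis as supportive, and the 95% intervals will show the precision achieved. Restating a planning figure would not add a biopsy or alter a test.

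The stale stratum wording is a carry-over from the protocol. SAP 3.1, 3.2.5.2 and Section 10 state plainly what will be tested and why, so an analyst would not be misled. Under Section 9's own effect and SD, the combined test has at least the primary test's 91.5% power, and even with no effect in an assumed 5 non-elevated patients per arm it would succeed about 90% of the time once the first test is passed. The primary between-arm power is untouched (91.5% at 22 per arm, 90.2% at 21). A sponsor revising the SAP for other reasons could add the assumptions, with correlations of both signs, but no result depends on it.

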10 CHANGES FROM PROTOCOL-SPECIFIED STATISTICAL ANALYSES

- The protocol specified 3 analysis populations for the study including the primary elevated C5b-9 population, the non-elevated C5b-9 population and the combined population. Due to the small sample size in the non-elevated C5b-9 stratum, the primary elevated C5b-9 population will remain as the primary population and the two strata combined (including both elevated and non-elevated C5b-9) will be considered the secondary population for analysis. Data from the non-elevated C5b-9 stratum will only be summarized.
- ITT population definition change to exclude subjects who had baseline C3G Histologic Index of activity score of 0.
- Secondary efficacy endpoint order rearranged.

12 APPENDICES

12.1 Data Derivation Details

12.1.1 EQ-5D-5L

Crosswalk value sets used in the calculation of the EQ-5D-5L Index Score are available for the following countries: Denmark, France, Germany, Japan, the Netherlands, Spain, Thailand, UK, US and Zimbabwe. For countries not listed above, reference data will used according to the following:

Country	EQ-5D-5L Crosswalk Value Country Set	
US, Canada	US	
Denmark, Sweden	Denmark	
France, Switzerland	France	
Germany, Czech Republic, Austria	Germany	
Japan	Japan	
Netherlands, Belgium	Netherlands	
Spain, Italy	Spain	
UK, Ireland, Australia, New Zealand,	UK	

12.2 Imputation for Missing/Partially Missing Adverse Event and Concomitant Medication Dates

12.2.1 Incomplete Adverse Event Start Date:

Partially missing AE start/stop dates will be imputed in the ADaM dataset for AEs, according to the rules below. However, listings of AE data will present the date as is, with missing date components left blank.

If the AE end date is complete with no missing year, month, or day, and a partially missing start date imputed by the rules below is after the AE end date, then the start date will be imputed by the AE end date.

Missing day and month

• If the year is the **same** as the year of the first dosing date, then the day and month of the first dosing date will be assigned to the missing fields.

- If the year is **prior to** the year of first dosing date, then December 31 will be assigned to the missing fields.
- If the year is **after** the year of first dosing, then January 1 will be assigned to the missing fields.

Missing day only

- If the month and year are the **same** as the year and month of first dosing date, then the first dosing date will be assigned to the missing day.
- If either the year of the partial date is **before** the year of the first dosing date or the years of the partial date and the first dosing date are the same but the month of partial date is **before** the month of the first dosing date, then the last day of the month will be assigned to the missing day.
- If either the year of the partial date is **after** the year of the first dosing date or the years of the partial date and the first dose date are the same but the month of partial date is **after** the month of the first dosing date, then the first day of the month will be assigned to the missing day.

Missing day, month, and year

• No imputation is needed. The corresponding AE will be included as TEAE.

12.2.2 Incomplete AE Stop Date:

If the imputed stop date is before the start date, then the imputed stop date will be equal to the start date.

Missing day and month

- If the year of the incomplete stop date is the **same** as the year of the last dosing date, then the day and month of the last dosing date will be assigned to the missing fields.
- If the year of the incomplete stop date is **prior to** the year of the last dosing date or prior to the year of the first dosing date, then December 31 will be assigned to the missing fields.
- If the year of the incomplete stop date is **prior to** the year of the last dosing date but is the same as the year of the first dosing date, then the first dosing date will be assigned to the missing date.
- If the year of the incomplete stop date is **after** the year of the last dosing date, then January 1 will be assigned to the missing fields.

Missing day only

- If the month and year of the incomplete stop date are the **same** as the month and year of the last dosing date, then the day of the last dosing date will be assigned to the missing day
- If either the year of the partial date is **not equal to** the year of the last dosing date or the years of the partial date and the last dosing date are the same but the month of partial date is **not equal to** the month of the last dosing date, then the last day of the month will be assigned to the missing day

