6.3 Adverse Events

Adverse event results will be provided including number of events and percentages of subjects (subject incidence) affected for the 3 Safety Populations (see 3.2.3 for definitions) separately including the following:

- All treatment emergent serious adverse events by SOC and preferred term
- All treatment emergent serious adverse events by decreasing order of frequency by preferred term
- All treatment emergent non-serious adverse events by SOC and preferred term
- All treatment emergent non-serious adverse events by preferred term by decreasing order of frequency
- All treatment emergent serious and non-serious adverse events by SOC

• All treatment emergent serious and non-serious adverse events by decreasing order of frequency by preferred term

Adverse events will be coded using the Medical Dictionary for Regulatory Activities (MedDRA) Version 20.1.

TEAEs for the Safety Population in each period are defined as an event with a start date on or after the first study drug treatment in each period and up to the final observation in each period. Treatment periods for analysis of adverse event are defined in Section 3.2.3. TEAEs for the All Avacopan Treated Population are defined as an event with a start date on or after the first dose of avacopan up to the final visit.

Adverse events will be listed by treatment group, including all available information of interest such as onset and resolution dates, study day of onset and resolution relative to first dosing day, duration, severity, seriousness, causal relationship to study medication per the investigator, action taken with study medication, and outcome. Separate listings will be provided for TESAEs, TESAEs and TEAEs leading to discontinuation of study drug, and TEAEs of interest.

TEAEs of interest include hepatic enzyme elevations, hypersensitivity Standardized MedDRA Queries (SMQ), infections, decrease in white blood cell count and elevations in creatine phosphokinase (CPK).

The severity of AEs was assessed by the investigator using the following protocol definitions:

- Mild (Grade 1): no limitation of usual activities
- Moderate (Grade 2): some limitation of usual activities
- Severe (Grade 3): inability to carry out usual activities
- Life-threatening (Grade 4): an immediate risk of death
- Death (Grade 5)

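### Adverse events with the day missing in the month of the Week 26 switch are dated before the switch, so in former placebo patients some early avacopan events count as placebo

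*SAP*

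**What the plan says.** SAP 12.2.1 sets the start-date rules: "Partially missing AE start/stop dates will be imputed in the ADaM dataset for AEs". Each rule compares the partial date with the first dosing date.

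- Day missing, month later than the first-dose month: "then the first day of the month will be assigned to the missing day". In the first-dose month itself, the first dosing date is used.
- Day and month missing, same year as the first dose: "then the day and month of the first dosing date will be assigned to the missing fields". For a later year, "then January 1 will be assigned to the missing fields".
- If the imputed start falls after a complete end date, "then the start date will be imputed by the AE end date". This can only move a start earlier.
- Start date wholly missing: "The corresponding AE will be included as TEAE", with no period named.

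SAP 6.3 tabulates events separately for the three safety populations of SAP 3.2.3. Each period's treatment-emergent events are those starting from that period's first dose to its final observation. For the third population: "TEAEs for the All Avacopan Treated Population are defined as an event with a start date on or after the first dose of avacopan". For a patient randomised to placebo, that dose is the Week 26 switch (Protocol 3.2 and 6.11, Day 183). Neither document compares a partial date with the switch.

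**The concern.** The tables have two boundaries, the first study dose and the first Period B dose, but the imputation rule knows only the first. At the first study dose the SAP settles same-month doubt towards treatment: the event is dated on the dosing day and counts as treatment-emergent. At the switch the rule settles the same doubt away from avacopan.

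What is at stake is the description of the first weeks on avacopan in patients who come to it from placebo. A misdated event in such a patient appears in the Period A placebo column and is absent from Period B and All Avacopan Treated. No efficacy result is touched.

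**Working it through.** The documents give no figure for partial dates, so there is none to reproduce. The check applies the SAP 12.2.1 rules to hypothetical dates.

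**Inputs.** Rules: SAP 12.2.1. Period definitions: SAP 3.2.3 and 6.3. Switch at Day 26 × 7 + 1 = 183, window ±7 days: Protocol 6.11. Last visit at Day 421: Protocol 6.22. Planned placebo patients: 22 per stratum, 44 in all (SAP 2.2.2). Assumptions: first-dose and onset dates are uniform over a four-year calendar cycle (1,461 first-dose dates), and no complete end date is available.

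**Example.** First dose 2019-03-14; switch 182 days later, 2019-09-12. True onset 2019-09-18, recorded as 2019-09. The imputed start is 2019-09-01, eleven days before the switch. In a placebo patient the event becomes a Period A placebo event and leaves both avacopan counts.

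**Day missing, switch month.** Let the month have L days and the switch fall on day d.

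- Days on or after the switch, summed over d: L(L+1)/2. All are misdated except the L days that arise when d = 1.
- Share misdated: 1 − L / [L(L+1)/2] = (L−1)/(L+1). For L = 30, 29/31 = 93.5%; for L = 31, 30/32 = 93.75%.
- Enumerated over the cycle: 21,520 / 22,981 = 93.6%. The 22,981 − 21,520 = 1,461 exceptions are the switches on the 1st.
- Days before the switch: 21,520, or 21,520 / (21,520 + 22,981) = 48.4% of switch-month days. None of these events moves to avacopan.

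**Day missing, by time since the switch.** For an onset j days after the switch (j below L), the misdated share is (L−1−j)/L, and zero beyond that. With L = 30:

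| Window after switch | Calculation | Enumerated |
|---|---|---|
| First 14 days | (29 − 6.5)/30 = 75.0% | 75.4% |
| First 28 days | (29 − 13.5)/30 = 51.7% | 52.4% |
| Day 183–421 (239 days) | 14.5/239 = 6.1% | 6.2% |

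Moving the switch by ±7 days leaves the enumerated shares unchanged.

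**Day and month missing.** Of events truly starting in Day 183–421, 67.1% are dated before the switch: 38.5% if the switch is in the first-dose year, 95.9% if it is in the next. The ±7-day window moves 67.1% to between 66.2% and 68.1%.

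**Size in patients.** The number k of missing-day events in the switch month among former placebo patients is not given. The expected number misassigned is 0.484 × k: about 0.5 for k = 1 and 2.4 for k = 5. One patient is 1/44 = 2.3% of all planned placebo patients, or 1/22 = 4.5% of one stratum.

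**After the change.** If switch-month dates take the first Period B dose date, the 93.6% falls to 0%. Pre-switch events in that month, 48.4% of its days, are then credited to avacopan unless a complete stop date shows otherwise.

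**The case against.** Exposure is probably small. Adverse events are recorded at Weeks 23, 26 and 28 (Protocol 6.10 to 6.12), and Week 28 is two weeks after the switch with a ±2-day window, so onset near the switch is closely bracketed. Serious events are reported within 24 hours (Protocol 7.2.6). Several events of interest in SAP 6.3 are laboratory-based, and the grade and shift tables of SAP 6.4 do not use imputed event dates. Listings show the partial date unaltered, so nothing is hidden. All of this stands.

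A second objection is that the fix reverses the error instead of removing it. With no stop dates, 21,520 onset days are misassigned under either rule. That is correct. The case for the change is the direction: it matches the SAP's own choice at the first study dose. A complete stop date before the switch can also correct an imputed date under the new rule, whereas under the present rule a stop date can only pull a start earlier.

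A reader might infer that the rule favours avacopan in the placebo-controlled comparison. The documents do not support that. The rule is the same in both arms, and in the avacopan arm it moves Period B events into Period A avacopan. The randomised Period A comparison is biased only if post-switch event rates differ between arms.

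A reader might also want year-only dates in placebo patients moved to the first Period B dose. When first dose and switch share a year, that would move every true Period A placebo event recorded by year only. Otherwise it would move about half. Each case covers about half of first-dose dates, so the total is about 0.5 × 100% + 0.5 × 50% = 75%. It would also treat the two arms differently.

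**Conclusion.** The point holds in a narrow form. A stated rule gives a one-directional wrong assignment for missing-day start dates in the calendar month of the switch. In former placebo patients, 93.6% of such events that truly began on avacopan count as Period A placebo and drop out of Period B and All Avacopan Treated. Later months are assigned correctly. Year-only dates have the same direction of error and a wider reach, but no simple single-date rule repairs them.

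The percentages rest on uniform first-dose and onset dates and on no informative stop date. The count affected is unknown and probably small. It would be wrong to infer that events around the switch are generally credited to placebo: fully dated events are unaffected, and wholly missing start dates are given no period at all. This is a cheap improvement to the safety tables, not a threat to the trial's conclusions.

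**What to change.** Add to SAP 12.2.1: when only the day is missing and the month and year equal those of the first Period B dose, the start date is the first Period B dose date, in both arms, unless a complete stop date is earlier. In that case the existing end-date rule applies. State also that an event dated on the day of that dose belongs to Period B, since the Week 26 visit may be both the last observation of Period A and the first dosing day of Period B.

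Leave the year-only rules as they are. Add a sensitivity tabulation that counts year-only events in Period A and then in Period B wherever the recorded year allows either.

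In the same edit, correct SAP 3.1.4, which points only to 12.2.2 (stop dates), and the second use of the number 12.2.1.

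The cost is two or three sentences, a short programming change and one small table, all of which can be specified while blinded. The downside is that some pre-switch events, up to about 48% of that month's days, are credited to avacopan.
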